3.4 Outcomes

COVID-19 vaccine effectiveness studies

The outcome of interest for the primary analysis is SARS-CoV-2 infection in patients of all ages hospitalised with SARI symptoms, laboratory-confirmed by PCR, documented either on admission to hospital or in the 14 days before admission.

Secondary outcomes of interest, in the same patient group, are laboratory-confirmed infections with genetic variants of SARS-CoV-2 and confirmed SARS-CoV-2 patients with severe outcomes (ICU admission, invasive ventilation or death).

Influenza vaccine effectiveness studies

The outcome of interest is laboratory-confirmed influenza in patients of all ages, hospitalised with SARI symptoms.

More specifically, this will be:

- subtype-specific laboratory-confirmed influenza A;
- laboratory-confirmed influenza B overall and, if available, by lineage (B Victoria/B Yamagata);
- laboratory-confirmed influenza by clade (where possible);
- laboratory-confirmed influenza co-infected with SARS-CoV-2 (where possible).

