3.5.5 SARI patients testing negative for SARS-CoV-2/influenza (test-negative controls)

A control will be defined as a hospitalised patient fulfilling the SARI case definition, with a respiratory sample negative for SARS-CoV-2 by PCR (for CVE) or a respiratory sample negative for influenza (for IVE) on admission to hospital.

It is advised that all sites test for both SARS-CoV-2 and influenza during the influenza season, as well as for all other respiratory viruses (as appropriate, depending on time of year), even if they are not participating in IVE. If this is not feasible, then during influenza season all samples that are negative for SARS-CoV-2 should also be tested for influenza (if not already tested at primary care level).

Controls that are negative by PCR but have Ct results suggestive of COVID-19⁶, and those with prior SARS-CoV-2 infection in the three months before admission, may be excluded as controls in sensitivity analyses (see Section 3.5.7 'Exclusion criteria').

- A study site/country measuring only CVE should indicate which testing strategy they will use (testing all samples for both SARS-CoV-2 and influenza, or only testing for influenza in those negative for SARS-CoV-2).
- > Each study site/country to indicate whether they can test for other respiratory viruses, only SARS-CoV-2 and influenza, or only SARS-CoV-2.

Other control groups (optional)

During periods when respiratory viruses are in low circulation, the number of SARI patients testing negative for SARS-CoV-2/influenza may be limited. Some sites may therefore wish to include other control groups, either in addition to SARI controls or as an alternative, and these must be recruited throughout the whole study period.

Examples of other control groups include:

- Patients testing PCR-negative to all respiratory viruses;
- Patients testing PCR-positive to respiratory viruses other than influenza (if IVE) or SARS-CoV-2, e.g. rhinovirus, respiratory syncytial virus (RSV), etc.; noting that patients with seasonal coronaviruses are excluded for CVE;
- Patients hospitalised with non-SARI related symptoms matched by time, age group and, if possible, underlying conditions:
 - Example source of hospitalised non-SARI cases: hospital wards admitting patients without COVID-19.
 Primary care: selection of GP patients belonging to the hospital catchment area and vaccination target
- group matched by time and age group:

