3.13 Analysis

3.13.1 Individual (country/study site level) analysis

The timing to conduct each interim analysis will depend on the time needed to achieve the appropriate sample size and regular updates are foreseen. This will depend mainly on the incidence of hospitalisation, COVID-19/influenza incidence, vaccination coverage, the recruitment strategy within hospital/s and the number of participating hospitals/services per hospital.

Cases and controls will be described by baseline characteristics. Patients will be described according to:

- sex;
- age group;
- time: month of symptom onset;
- COVID-19 (CVE)/influenza (IVE) vaccination status;
- absence/presence of at least one, presence of more than one high-risk condition;
- specific chronic conditions (e.g. diabetes, respiratory, cardiovascular diseases, immunodeficiency);
- pregnancy;
- vaccination status of other vaccines;
- respiratory co-infections (where available);
- severity (ICU, oxygen use, invasive ventilation, death);
- SARS-CoV-2 variant/influenza (sub)type and clade (where possible) for cases;
- vaccine product (for vaccinated cases).

A sample layout of this descriptive analysis is provided in Table 6 below.

Table 6. Example of descriptive table for cases and controls; COVID-19/influenza hospital-based vaccine effectiveness study, ECDC multi-centre study, 2023

Variables	iables Number of laboratory-confirmed COVID-19 (or influenza) cases/total n (%)		
Median age (IQR)	X	Х	
Missing	X	X	
Age groups (years)			
20–59	x/x (x)	x/x (x)	
60–79	x/x (x)	x/x (x)	
≥ 80	x/x (x)	x/x (x)	
Missing	X	X	
Sex			
Female	x/x (x)	x/x (x)	
Missing	X	X	
Days between onset of symptoms and swabbing			
0	x/x (x)	x/x (x)	
1	x/x (x)	x/x (x)	
2	x/x (x)	x/x (x)	
3	x/x (x)	x/x (x)	
4–7	x/x (x)	x/x (x)	
COVID-19/influenza vaccination	x/x (x)	x/x (x)	
Missing	X	X	
etc.			

This study is a case—control study (test-negative design). The measure of association is the odds ratio (OR). This can be estimated by logistic regression. An OR = 1 indicates no association between an exposure and the outcome. An OR > 1 indicates a potential risk factor, an OR < 1 indicates a potential protective factor, noting that the confidence interval around the OR helps with its interpretation.

For vaccination as a preventive factor, the CVE/IVE can be computed as CVE/IVE = (1 - OR)*100. A 95% confidence interval is computed around the point estimate.

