3.13.2 Sensitivity analyses

As sensitivity analyses, study sites can measure CVE/IVE:

- with different cut-offs of numbers of days between onset and swab;
- with different cut-offs of numbers of days between vaccination and symptom onset;
- with varying the post-vaccination periods (e.g. 7 days, 14 days, etc.) to be considered 'completely vaccinated' or 'partially vaccinated' (see Section 3.8.1);
- including, excluding, stratifying or adjusting by previous positive test status, and also by different delays between prior test and inclusion in the study:
- excluding patients testing positive prior to hospitalisation but negative in hospital;
- · using only controls positive to other respiratory viruses;
- excluding controls testing SARS-CoV-2 positive (IVE) or influenza positive (CVE), or adjusting by COVID-19 vaccination (see also Section 5.1.7);
- using different reference groups for VE estimation (e.g. for CVE: unvaccinated people, people vaccinated with a smaller number of doses, people vaccinated in the previous season).
- 3.13.3 Pooled analysis.

The higher sample size for the pooled analysis will provide more precision around the VE estimates. Data can be coded as outlined in Annex 1, or a codebook can be provided by the study teams that includes the variable names, descriptions and coding. The central hub will perform data cleaning and document and share any further data cleaning and analysis with all study coordinators to ensure it can be reproduced.

See Annex 2 for details of the pooled analysis plan. For the pooled data, interim analyses will be conducted during different periods, if appropriate, and according to the available sample size.

The timing to conduct each interim analysis will depend on the time needed to achieve the appropriate sample size. This will depend mainly on the incidence of hospitalisation, COVID-19/influenza incidence, vaccination coverage, the recruitment strategy within hospitals and the number of participating hospitals/services per hospital.

The pooled analysis will be carried out in a similar way to the site-specific analysis. Country or study site will potentially be included as a fixed effect, or as a random effect in a multi-level model. Statistical heterogeneity between study sites will be determined in a two-stage analysis using the Q-test and the I² index [30].

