5.1.7 Inclusion of influenza-positive controls for CVE and SARS-CoV-2-positive controls for IVE

A key prerequisite of the test-negative design is that the vaccination of interest does not affect the control group. However, there may be a strong correlation between those receiving influenza and COVID-19 vaccines, which would introduce bias. For example, if inclusion of SARS-CoV-2-positive controls artificially lowers the vaccine coverage among influenza test-negative controls, there would be a bias towards a lower IVE. Similarly, inclusion of influenza-positive controls in CVE may artificially lower the vaccine coverage among SARS-CoV-2 test-negative controls, biasing towards a lower CVE. The test-negative design would no longer be valid.

To account for this, analyses should be carried out excluding SARS-CoV-2 controls (IVE) and influenza controls (CVE), if adequate information is available [31]. These estimates can be compared with the primary analysis including SARS-CoV-2/influenza controls.

Sensitivity analyses will be conducted, excluding controls who are positive for influenza from CVE estimation and controls who are positive for SARS-CoV-2 from IVE estimation.

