This study is a case—control study (test-negative design). The measure of association is an odds ratio (OR). This can be measured by logistic regression. An OR = 1 indicates no association between an exposure and the outcome. An OR > 1 indicates a potential risk factor, an OR < 1 indicates a potential protective factor, noting that the confidence interval around the OR helps with its interpretation.

For vaccination as preventive factor, the VE can be computed as VE = (1 - OR)*100. A 95% confidence interval is computed around the point estimate.

Pooled univariable analyses (VE estimates from crude OR)

Baseline characteristics of cases and controls will be compared using the chi-square test, Fisher's exact test, t-test or the Mann-Whitney test (depending on the nature of the variable and the sample size). The association (OR) between vaccination status and baseline characteristics will be measured for both case and control groups.

Stratified analysis

Depending on sample size, the analysis by vaccine product will be further stratified according to:

- sex:
- age group, e.g. 0–14 years, 15–49 years, 50–64 years, 65–79 years, 80+ years;
- specific chronic conditions (e.g. respiratory disease, diabetes, immunodeficiency⁹);
- absence, presence of at least one, presence of more than one high-risk condition;
- time: this will depend on timing of the pandemic/influenza season at sites/in countries and may just include one period at the start of the study once vaccines are available, and a specified period later on;
- dose (for CVE): partial vaccination, full vaccination, full vaccination plus booster;
- swab delay (0–3 days, 4–7 days; 8+ days);
- vaccination delay (<8 days, 8–14 days, >14 days, etc.);
- hospital admission delay (0-4 days, 5-9 days, 10 days +, onset after hospitalisation);
- previous vaccination against influenza and pneumococcal disease;
- prior infection with influenza or SARS-CoV-2 (prior to hospital admission for SARI);
- current co-infection with influenza (for CVE) or SARS-CoV-2 (for IVE) or other respiratory viruses (for both CVE and IVE);
- severity (ICU admission, ventilation/oxygen, death; for CVE);
- CVE/IVE at different time points in calendar time, e.g. by week or group of weeks (e.g. CVE for weeks 2–20, 21–42, etc.; IVE for interim season (to end January), and for the whole season);
- for the various groups of vaccines (if available/applicable), mode of injection (intradermal vs intramuscular);

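### The co-infection outcome for influenza vaccine effectiveness has no comparator of its own; with the only stated control group it would absorb part of the COVID-19 vaccine's effect if the two vaccinations are positively correlated

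*Protocol*

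**What the plan says.** Section 3.4 (Outcomes) gives the specific IVE outcomes. The last is "laboratory-confirmed influenza co-infected with SARS-CoV-2 (where possible"). It names no comparator.

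Section 3.5.5 defines an IVE control as a SARI patient with "a respiratory sample negative for influenza (for IVE) on admission to hospital". It sets no SARS-CoV-2 condition and no separate rule for the co-infection outcome. Section 3.13.1 fixes the effect measure: "The measure of association is the odds ratio (OR"), with effectiveness taken as one minus that ratio.

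Section 5.1.7 deals with correlated vaccination: "there may be a strong correlation between those receiving influenza and COVID-19 vaccines, which would introduce bias". It describes the effect on controls, where the bias lowers IVE, and responds that "analyses should be carried out excluding SARS-CoV-2 controls (IVE) and influenza controls (CVE), if adequate information is available". It adds that "These estimates can be compared with the primary analysis including SARS-CoV-2/influenza controls", so SARS-CoV-2-positive controls stay in the primary IVE analysis.

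Three other provisions bear on the point:
- Section 3.13.2 offers sites, as an optional sensitivity analysis, "excluding controls testing SARS-CoV-2 positive (IVE) or influenza positive (CVE), or adjusting by COVID-19 vaccination (see also Section 5.1.7").
- Annex 2 (Stratified analysis) lists, depending on sample size, "current co-infection with influenza (for CVE) or SARS-CoV-2 (for IVE) or other respiratory viruses (for both CVE and IVE").
- Annex 2 (Multivariable analysis) asks for sex, age and onset time always to be in the model where possible. COVID-19 vaccination is not in that minimum set.

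**The concern.** A test-negative comparison needs cases and controls to differ only in the virus under study. Here a case must carry two viruses, but the stated control only has to be free of one of them. SARS-CoV-2 positivity is then a selection condition on cases that most controls may not share. If the COVID-19 vaccine works, SARS-CoV-2-positive patients are less often vaccinated against COVID-19. If uptake of the two vaccines goes together, they are also less often vaccinated against influenza. The odds ratio for the influenza vaccine would then include some of the COVID-19 vaccine's protection.

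Section 5.1.7 recognises the correlation but follows it only through the controls. For this outcome the distortion arises in the cases and runs the opposite way, towards higher IVE. At stake is a sub-outcome estimate that could look protective with little or no influenza vaccine effect behind it.

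**Working it through.** The protocol states no figure for this outcome, so there is nothing to reproduce. It also gives no CVE, no strength of correlation and no share of SARS-CoV-2-positive controls. Those inputs are assumptions, shown as a range.

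**Inputs (all assumed)**
- Influenza vaccine coverage 50%.
- CVE: 40%, 50%, 60%.
- COVID-19 vaccination in influenza-vaccinated (a) v influenza-unvaccinated (b) patients: 60% v 30% or 80% v 20%.
- Share s of influenza-negative controls who are SARS-CoV-2-positive: 0% (as after the section 5.1.7 exclusion) or 20%.
- The two infections are independent given vaccination. The analysis is crude.

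**Formulas**
1. Ratio of SARS-CoV-2 positivity, influenza-vaccinated to unvaccinated: R = (1 − CVE × a) / (1 − CVE × b).
2. Odds of influenza vaccination in co-infected cases, at 50% coverage: R × (true influenza OR).
3. Proportion influenza-vaccinated among controls: p = (1 − s) × 0.5 + s × R/(1 + R). Control odds = p/(1 − p).
4. Apparent IVE = 1 − (line 2)/(control odds).

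**Worked case**, CVE 50%, 80% v 20%, true IVE 0:
- R = (1 − 0.40)/(1 − 0.10) = 0.60/0.90 = 0.667.
- With s = 0, the control odds are 1, the OR is 0.667 and apparent IVE is 33%.
- With s = 20%, p = 0.8 × 0.5 + 0.2 × 0.40 = 0.48, the control odds are 0.48/0.52 = 0.923, the OR is 0.667/0.923 = 0.722 and apparent IVE is 28%.

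**Apparent IVE when the true value is 0**

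| CVE | COVID-19 vaccination, a v b | R | s = 0% | s = 20% |
|---|---|---|---|---|
| 40% | 60% v 30% | 0.76/0.88 = 0.864 | 14% | 11% |
| 50% | 60% v 30% | 0.70/0.85 = 0.824 | 18% | 14% |
| 60% | 60% v 30% | 0.64/0.82 = 0.780 | 22% | 18% |
| 40% | 80% v 20% | 0.68/0.92 = 0.739 | 26% | 21.5% |
| 50% | 80% v 20% | 0.60/0.90 = 0.667 | 33% | 28% |
| 60% | 80% v 20% | 0.52/0.88 = 0.591 | 41% | 34.5% |

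If the true IVE is 50% and CVE is 50%, the readings are 67% (s = 0) and 64% (s = 20%) at 80% v 20%, and 59% and 57% at 60% v 30%.

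**Boundary check.** If a = b, or if CVE = 0, then R = 1 and the bias is zero.

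**Cross-check with a different parameterisation.** The correlation was set through an odds ratio between the two vaccinations of 3 to 20, with CVE 30–70%, influenza/COVID-19 coverage from 30%/30% to 75%/70%, and 20% of controls SARS-CoV-2-positive. A null vaccine then reads about 6% to 44%.

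**Effect of the section 5.1.7 exclusion.** With coverage 50%/50%, vaccination odds ratio 10 and CVE 50%, a null vaccine reads 24.5% with 20% SARS-CoV-2-positive controls and 29.5% once they are dropped. The exclusion removes the only controls who share the cases' selection. In the same setting, influenza without co-infection reads −7.2%, the direction that section 5.1.7 describes.

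**Effect of the two remedies.** Within SARS-CoV-2-positive patients, R applies to cases and controls alike and cancels. Within a COVID-19 vaccination stratum, the factor (1 − CVE) is the same for influenza-vaccinated and unvaccinated patients and cancels. Both give 0% when the true IVE is 0. With a true IVE of 40% (coverage 50%/50%, vaccination odds ratio 10, 20% SARS-CoV-2-positive controls) both return 40%, while the ordinary controls give 48%, 55% and 62% at CVE 30%, 50% and 70%.

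**The case against.** The strongest reply is that the faulty analysis is never written down. Section 3.4 lists an outcome, section 3.5.5 is generic, and the Annex 2 stratified analysis that names co-infection may already be the sound one. This partly stands: pairing section 3.4 with section 3.5.5 is an inference. But section 3.5.5 is the only test-negative control definition given for IVE. Annex 2 does not spell out its contrast, and reading it as influenza-positive v influenza-negative among SARS-CoV-2-positive patients is also an inference.

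A second reply is that adjustment is available and that covariates can be left to an analysis plan. Section 3.13.2 mentions adjusting for COVID-19 vaccination, and Annex 2 offers IVE by recent COVID-19 vaccination where numbers allow. Either would remove or greatly reduce the bias if applied here. None is tied to this outcome, and the measure that section 5.1.7 recommends for correlated vaccination enlarges the error. The outcome, the control definition and that measure are all set in this protocol.

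A third reply is that the figures are crude and assumed. That stands. The 80% v 20% scenario is a strong association (odds ratio 16), and adjustment for age, sex and onset time would remove some of any correlation due to shared age targeting.

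Stronger readings are tempting but unsupported. A reader might infer that the protocol asserts a strong correlation; section 5.1.7 says only that there may be one. A reader might infer that a false result would pass straight into co-vaccination advice; nothing in the protocol links this outcome to such advice.

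**Conclusion.** The point holds in a conditional form. As the text stands, IVE against co-infection has one stated control group, and that group does not share the cases' SARS-CoV-2 positivity. With positively correlated vaccination and CVE above zero, the estimate is biased upwards. The direction does not depend on the exact inputs. The size does: about 11–41% for a null vaccine over the range assumed, in a crude analysis with the infections independent given vaccination.

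The scope is narrow. This is one sub-outcome, to be studied only where possible, and the Annex 2 minimum sample-size criteria may keep it from being reported at all. A reader might infer that IVE in general is inflated. It is not: the main IVE estimate is not inflated by this mechanism. The point deserves correction because the change is small and because following section 5.1.7 faithfully would make this estimate worse.

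**What to change.** State in section 3.4 that IVE against co-infection is estimated in one of two ways, and say which is primary:
- with all influenza-negative controls, adjusted for current COVID-19 vaccination as defined in section 3.8.1; or
- within SARS-CoV-2-positive SARI patients, comparing influenza-positive with influenza-negative, with the Annex 2 stratum worded to match.

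Add that the section 5.1.7 exclusion of SARS-CoV-2-positive controls does not apply to this outcome.

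The cost is a sentence or two and a cross-reference. Annex 1 already carries COVID-19 vaccination dates and the SARS-CoV-2 and influenza results. The restricted version has fewer controls and so a wider interval for an outcome likely to be sparse. It also needs SARS-CoV-2 results for influenza-negative patients, and section 3.5.5 advises testing for both viruses without guaranteeing it. The adjusted version keeps all the controls but relies on complete COVID-19 vaccination data.

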3.5 Definitions

3.5.1 Hospitalised patient

A hospitalised patient is one who has been admitted to one of the participating hospitals during the study period and has not been discharged to their home or home equivalent, or died within 24 hours.

3.5.2 SARI patient

A SARI patient is defined as a hospitalised person with at least one of the following symptoms:

- cough;
- fever;
- shortness of breath;
- sudden onset of anosmia, ageusia or dysgeusia.

SARI patients with onset of symptoms in the 14 days prior to hospital admission will be included in the study. Note that hospitals already participating in SARI surveillance systems should not modify the SARI inclusion criteria for surveillance. However, for the CVE analysis, only those patients with onset of symptoms in the 14 days prior to hospital admission will be included.

In a later protocol version, a cut-off for days between onset of symptoms and swabbing may be decided (if appropriate).

A SARI patient is defined using ECDC's clinical case definition for a hospitalised possible COVID-19 case³. Compared with the World Health Organization (WHO) SARI case definition⁴ (an acute respiratory infection with a history of fever or measured fever of ≥38 C° and cough, onset within the last 10 days and requiring hospitalisation), ECDC's possible COVID-19 case definition is more sensitive. Each study site/country will report individual SARI symptoms separately to allow sensitivity analyses comparing CVE and IVE estimates, based on alternative SARI case definitions and depending on the pathogen.

3.5.3 SARI patients confirmed as COVID-19

A confirmed COVID-19 case will be defined as a hospitalised patient fulfilling the SARI case definition, with a respiratory sample positive for SARS-CoV-2 by PCR, [29] either on admission to hospital or documented in the 14 days prior to hospital admission.

3.5.4 SARI patients confirmed as influenza

A confirmed influenza case will be defined as a hospitalised patient fulfilling the SARI case definition, with a respiratory sample PCR-positive for influenza⁵.

³ ECDC possible COVID-19 case definition: https://www.ecdc.europa.eu/en/covid-19/surveillance/case-definition

⁴ WHO SARI case definition: https://www.who.int/teams/global-influenza-programme/surveillance-and-monitoring/case-definitions-for-ili-and-sari

⁵ No requirement for the dates of the test. There are additional requirements in the exclusion criteria relating to test date and symptom onset.

